10.5 Analysis of the Primary Efficacy Endpoint(s)

For the primary efficacy endpoint, time to sustained clinical recovery from study day 1 onward will be compared using a Gehan Wilcoxon test.

The primary analysis of the primary efficacy endpoint will be based on the Modified Intent to Treat Population (mITT), defined as any subject randomized into the study and took at least one dose of study medication (excluding subjects who qualified for enrollment based upon changes in taste and smell).

Additional primary efficacy endpoint analyses will also be performed using the mITT, mITT2, and the Per Protocol populations. Every effort will be made to ensure that subjects are followed until hospitalization, death, or 28 days post treatment start, whichever happens first. Subjects who were hospitalized or died will be assumed to have not met the primary endpoint in the primary analysis.

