9.2 Study Procedures

9.2.1 Screening, Baseline, Randomization and Treatment (Day 1)

The following procedures will be performed at the Day 1 in-person visit:

- Confirmation of positive SARS-CoV-2 test result
- Confirm subject meets all inclusion and none of the exclusion criteria
- Review the study with the subject and obtain written informed consent and Health Insurance Portability and Accountability Act of 1996 (HIPAA) authorization, or equivalent in another respective country, as applicable such as *Lei Geral de Proteção de Dados Pessoais (LGPD)* in Brazil
- Register the subject in IWRS to allot a unique subject ID (screening number)
- Randomize subject to treatment arm in IWRS as per randomization schedule
- IWRS to assign unique randomization number to the subject
- IWRS to assign IP kit number as per randomization schedule
- Record demographics (age, race, ethnicity, gender)
- Review and record medical history, surgical history
- Review and record smoking, alcohol and medication history
- Document all current medications, including medications over the counter and herbal medications
- Record height and weight
- Record COVID-19 symptoms for inclusion
- Record confirmation of positive SARS-CoV-2 test result
- Record number of days since onset of symptoms
- Collect blood sample for below listed blood tests:
 - CBC with differential, Electrolytes, BUN, Creatinine, Random Blood Serum Glucose, AST, ALT, Bilirubin, uric acid, SARS-CoV2 IgG, IL-6, IL-10, ESR, CRP, D-Dimer, ferritin. (CRP = C-reactive protein, IL-6 = Interleukin-6, IL-10 = Interleukin-10, CBC = Complete Blood Count).
 - Site do not require to wait for blood test result to randomize subjects.

- Provide the allotted IP kit, the blinded treatment (either favipiravir or placebo), and other study materials to the subject
- Assist the subject in downloading the ePRO app, create ePRO credentials for the subject, train the subject on how to use the ePRO and enter the Day 1 Dose 1 visit data with the subject during the visit to ensure the subject's understanding.
- Until the sub-study enrollment is completed (112 events have been counted), all subjects will be enrolled into the viral shedding sub-study. However, if they choose so, subjects can opt-out of participating in the viral shedding sub-study.

9.2.2 Treatment Day 1 to Day 10

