10.2 Sample Size Considerations

10.2.1 Sample Size Determination: study's primary endpoint: time to sustained clinical recovery by Study Day 28

Group sample sizes of approximately 625 in each treatment group (Favipiravir and placebo) to get at least 815 clinical recoveries will achieve sufficient power to detect a clinically meaningful effect size using a two-sided Wilcoxon test at an overall significance level of 0.05.

10.2.2 Sample Size Justification: study's primary endpoint: time to sustained clinical recovery by Study Day 28

A review of the medical literature including descriptive and intervention studies reveals variation in the estimate of 'median time to symptom alleviation'. There is lack of consistency among studies in regard to: 1) the definition used for 'symptom alleviation', 2) the reference time point (some use the day of first symptoms, the day of first positive PCR test, the day of study enrollment, and the day of hospitalization, 3) the length of follow up. To account for the uncertainty surrounding the estimate of 'median time to symptom alleviation', we performed a series of intermediate sample size calculations for a variety of likely scenarios with median times to sustained clinical recovery for the control group ranging from 3 to 15 days and median times to sustained clinical recovery for the favipiravir group ranging from -1 to -6 days (when possible) as compared to the control group. The worst case of those scenarios was retained to establish the definitive sample size estimation for the trial.

The definitive sample size assessment is based on a group sequential design with a possibility to stop for efficacy and for futility (unbinding rule) at interim, once 45% of the information is obtained (i.e. 367 events), using Power family ($\Phi=1.147$) alpha and beta spending functions. Assuming proportional hazards, a median time of 5 days in the control group vs. a median time of 4 days in the favipiravir group (which provide a hazards ratio of 1.25) and controlling for an overall alpha of 5% (two-sided), it is estimated that about 475 participants per group would be required to obtain a total of **815 clinical events** (defined as clinical recoveries). This will ensure a power of 85% to detect a difference between the two groups in terms of time to clinical recoveries by Day 28.

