10.8.3 Sub-Group Analyses

- 1) Status at enrollment defined as Seronegative (negative IgG) vs. Seropositive (positive IgG).
- 2) Age at enrollment: Age \geq 50 years vs. Age $<$ 50 years and Age \geq 60 years vs. Age $<$ 60 years.
- 3) Time from first positive SARS-CoV-2 test to enrolment (<2 days from their first positive COVID test vs. $>$ 2 days).
- 4) Risk-status of COVID-19 progression (high risk vs. others). High-risk for COVID-19 progression is defined as patients who meet at least one of the following criteria: 1) Overweight (BMI \geq 25), 2) Chronic kidney disease, 3) Diabetes Mellitus, 4) Weakened immune system, 5) Currently receiving immunosuppressive treatment, 6) \geq 65 years of age, 7) Pregnancy, 8) Cardiovascular disease/hypertension, 9) Chronic lung disease, 10) Sickle cell disease, 11) Neurodevelopmental disorders, 12) Medical-related technological dependence
- 5) Ethnicity (Hispanic vs. non-Hispanic).
- 6) Magnitude of symptoms at enrollment (high, defined as having a minimum of 4 symptoms at a level of moderate or severe on study day 1 vs. low, defined as having $<$ 4 moderate or severe symptoms on study day 1).

- 7) Status of receiving SARS-CoV-2 monoclonal antibodies treatment after study enrolment (Yes, No).
- 8) Status of study-drug adherence (drug adherence >80% defined as: the subject took at least 72 study-drug pills as documented in ePRO and/or EDC vs. ≤ 80%). For calculation purposes: day 1 dose 1 and dose 2 are 9 pills each, all other study doses are 4 pills.
. Detailed analysis will be described in SAP.
- 9) Level of highest RNA load on study day 1 or 2 or 3: high versus vs. all other and very high versus all other. High and very high RNA loads are defined as RNA load of >1,000 or >10,000, respectively.
- 10) Type of SARS-CoV-2 variant: Alpha (B.1.1.7), Beta (B.1.351, B.1.351.2, B.1.351.3), Delta (B.1.617.2, AY.1, AY.2, AY.3), or Gamma (P.1, P.1.1, P.1.2).
- 11) Status of C-reactive Protein level (abnormally elevated vs. normal) at baseline.
- 12) Status of D-dimer level (abnormally elevated vs. normal) at baseline.
- 13) Status of C-reactive Protein level and D-dimer (both are abnormally elevated vs. other) at baseline.

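### The primary Gehan test is unstratified although plausible prognostic factors are recorded on Day 1; the test is valid but may give up some power

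*Combined protocol and SAP*

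**What the plan says.** - **Primary test.** Section 10.5: "time to sustained clinical recovery from study day 1 onward will be compared using a Gehan Wilcoxon test". Section 10.4 names the same test. Neither gives a stratum, a covariate or an adjusted supportive model. Sections 5.1 and 7.3 describe 1:1 allocation and state no stratification factor.
- **Design basis.** Section 10.2 assumes "a median time of 5 days in the control group vs. a median time of 4 days in the favipiravir group". It takes the treatment HR from these medians as 1.25, and plans about 625 per arm "to get at least 815 clinical recoveries will achieve sufficient power". Of the 815-event design it says: "This will ensure a power of 85% to detect a difference between the two groups".
- **Baseline data.** The Day 1 list in section 9.2.1 includes "Record number of days since onset of symptoms" and the symptom record used for inclusion. Section 10.8.3 already has a cut-point for burden: "Magnitude of symptoms at enrollment (high, defined as having a minimum of 4 symptoms at a level of moderate or severe", but uses it only for a subgroup. Days since onset is not in that subgroup list; time from first positive test is.
- **Further detail.** Sections 10.8.1, 10.8.5 and 10.9 refer to SAP 3.1, whose text is not part of the document reviewed.

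**The concern.** Recovery requires every one of twelve symptoms to be mild or absent. A subject who enters with six symptoms above mild has more to resolve than one who enters with two, so burden at entry plausibly predicts time to recovery. Days since onset is plausible for a similar reason.

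If such a factor matters and the test ignores it, two things happen. The pooled treatment contrast is pulled toward no effect, and variation between subjects adds noise. A stratified test compares like with like and avoids both.

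The stake is wider than one endpoint. The hierarchy in section 10.6 starts with clinical recovery. If that test misses, neither progression endpoint can be claimed.

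**Working it through.** **1. Reproduce the design.** Inputs from sections 10.2 and 10.8.2: HR 5/4 = 1.25, two-sided alpha 0.05, power 85%, one look at 45% information, power-family spending with parameter 1.147.

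- Fixed design (Schoenfeld): 4 × (1.960 + 1.036)² / (ln 1.25)² = 4 × 8.98 / 0.0498, or 722 events after rounding up.
- Interim alpha: 0.05 × 0.45^1.147 = 0.0200. The matching final nominal level is 0.0369. Both agree with the plan.
- Two-stage design, with a futility stop counted as lost power: 820 events against 815 stated. Power at 815 is 84.8% against 85% stated.

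The design therefore reproduces without any prognostic factor.

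**2. Compare the two tests by simulation.** The stratified statistic is Z = Σₛ Σⱼ w(d₁ − dY₁/Y) / √(Σₛ Σⱼ w²V). Here Y is the number at risk in stratum s on day j, V is the hypergeometric variance, and w = Y/nₛ.

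Assumptions, first set-up: exponential recovery, control median 5 days, treatment HR 1.25, 13% never recovering, daily assessment to Day 28, 625 per arm, final two-sided level 0.0369. The 13% and the factor HRs are not in the documents. Entries are power (%), unstratified v stratified.

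| Factor HR | One 50/50 factor, run 1 | One 50/50 factor, run 2 | Four strata | Gain (points) |
|---|---|---|---|---|
| 1.0 | – | 69.4 v 69.4 | 70.2 v 70.3 | about 0 |
| 0.7 | 68 v 69 | 70.3 v 71.4 | 67.8 v 69.9 | 1 to 3 |
| 0.55 | 67 v 70 | 65.7 v 69.8 | 65.4 v 70.3 | 3 to 5 |
| 0.4 | 63 v 71 | 62.2 v 71.3 | 61.2 v 70.0 | 8 to 9 |

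With 2,500 trials, as in the one-factor runs, a power near 70% has a standard error of √(0.7 × 0.3 / 2500) = 0.9 points, so small differences between columns mean little. With no treatment effect, the four-stratum comparison rejected 3.2 v 3.7% against a nominal 3.69%.

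**3. Is the gain an artefact of the 13%?** Second set-up: 1,250 subjects, nobody permanently unrecovered, 65.2% recovered by Day 28 (about 815 events), two balanced factors, single test at two-sided 0.05, 3,000 trials per case. HRs above 1 here mean faster recovery.

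| Factor HRs | Unstratified v stratified (%) | Gain (points) |
|---|---|---|
| 1.0, 1.0 | 86.8 v 86.6 | −0.2 |
| 1.3, 1.3 | 84.8 v 85.5 | 0.7 |
| 1.5, 1.5 | 83.5 v 84.9 | 1.4 |
| 2.0, 2.0 | 81.0 v 85.5 | 4.5 |
| 3.0, 2.0 | 75.6 v 84.2 | 8.6 |

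The gain follows the same pattern, and base power is now close to the plan's. The level in step 2 therefore comes from the 13% assumption. Setting it to zero in step 2 at factor HR 0.7 gives about 90% unstratified and 91.5% stratified. Only the gap between the two tests belongs to this point.

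**4. Cost if the factors are useless.** Relative efficiency of the four-stratum test was 0.995 to 0.996, a loss of about 0.5% of information.

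**5. The same question as an information calculation.** If baseline factors explain a share R² of the Gehan-score variance, information rises by 1/(1 − R²), and the events needed for 85% power become 815 × (1 − R²). From a start of 85% power:

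- R² = 0.02: 85.7%, 799 events.
- R² = 0.05: 86.7%, 775 events.
- R² = 0.10: 88.5%, 734 events.
- R² = 0.20: 91.7%, 652 events.

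This takes 85% as the unadjusted power. Steps 2 and 3 fix HR 1.25 within strata, so there the unadjusted power falls and stratifying restores it.

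**The case against.** The strongest reply is that the unadjusted test is valid under 1:1 allocation with no stated strata, and that nothing in the documents measures how well any factor predicts recovery. The one prognostic statement, in section 3.1, concerns age and comorbidity and progression to severe disease. Eligibility also narrows both proposed factors: at least two symptoms scored 2 or higher, and onset no more than 5 days before randomization. All of this stands. It makes the gain conditional, but leaves the choice lopsided, because the loss is negligible if the factors are useless.

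The practical objections also stand and shape the fix:

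- The mITT definition in section 10.3 sets no Day 1 ePRO symptom requirement (mITT2 does), so some ePRO-based strata could be missing.
- The endpoint counts from Day 1, so a Day 1 ePRO score could serve as both stratifier and outcome.
- The nominal levels 0.02 and 0.0369 presume one statistic at both looks, and the documents do not say whether the interim look has taken place.
- SAP 3.1 may already contain an adjusted analysis.

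A reader might infer that these are strong predictors and that the power comes free. The documents support neither: strength is unknown, and the change needs extra rules. A reader might also infer from the 61 to 70% base power that the trial falls short of 85% because it does not adjust. Step 3 shows otherwise. Conversely, one might assume that the regulator agreed the unstratified test. The amendment history attributes several changes to the FDA, but none concerns the choice of test.

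**Conclusion.** The point holds as one of efficiency; no bias or type I error problem is shown. Section 10.5 leaves out stratification on baseline values that are already collected. With 625 per arm the expected gain runs from about 0 to 9 points of power, depending on assumed factor HRs between 1.0 and 0.4. Confidence is high that the current text specifies no adjustment and that stratifying keeps the type I error. It is only moderate on the size of the gain, because no prognostic strength for recovery time is documented. Blinded pooled data could check that strength without revealing treatment effects.

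**What to change.** State in section 10.5, and carry into the SAP:

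- **Test.** The primary test is the Gehan Wilcoxon test stratified by baseline symptom burden (at least 4 v fewer than 4 moderate or severe symptoms) and days since symptom onset (0–2 v 3–5).
- **Source.** Burden comes from the symptom record made for inclusion, before randomization. Sections 5.1 and 7.3 require eligibility to be confirmed before randomizing, so this record should exist for every subject.
- **Missing values.** Give a rule, for example assignment to the larger category.
- **Consistency.** Use the same statistic at the interim and final analyses, fixed before unblinding.
- **Supporting analysis.** Keep the unstratified test as a sensitivity analysis.

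If an interim look has already used the unstratified test, either keep that test as primary or confirm the boundaries, and report the stratified test as a pre-specified supportive analysis.

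The cost is protocol and SAP wording, the missing-value rule, and about 0.5% of information if the factors turn out not to be prognostic. No new data are needed. Check SAP 3.1 first; if it already stratifies, section 10.5 should say so.

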10.6 Analysis of the Key Secondary Endpoint(s)

Proportion of subjects with COVID-19 progression will be presented with counts and percentage. Significance among group will be evaluated using Chi-square test or Fisher test as applicable. The corresponding confidence interval for the difference in proportions will be calculated.

Viral shedding sub-study (time in number of days to negative conversion of detectable SARS-CoV-2 viral RNA to undetectable viral RNA in RT-PCR assays of saliva, from start of study treatment to date of last viral assessment) will be analyzed using time-to event methods.

All secondary endpoint analyses will be performed for the mITT, mITT2 and PP populations.

Adjustment for multiple testing will be performed to control the overall type 1 error to no more than 5% for the interim and final analysis on the primary efficacy endpoint.

Moreover, for labeling purposes, a hierarchical approach will be used to control the overall type 1 error to $\leq 5\%$ for the primary and key secondary endpoints. The order of testing will be:

1. Clinical recovery
2. Broad progression (key secondary endpoint)
3. Narrow progression (key secondary endpoint)

Statistical significance cannot be claimed if the parameter on top of the parameter being tested did not reach statistical significance. For example, if clinical recovery was not statistically significant at final analysis, the other parameters will not be considered as having reached statistical significance (no matter the results obtained). If clinical recovery reaches statistical significance at final analysis and Broad progression (key secondary endpoint) does not, the remaining parameters will not be considered as having reached statistical significance and so on.

10.6.1 Additional Secondary Efficacy Analysis

The additional secondary endpoint of time to negative conversion of positive SARS-CoV-2 (viral culture assays of saliva) will be analyzed as described in the statistical analysis plan (SAP version 3.1).

The additional secondary endpoint analyses will be performed for the mITT, mITT2, and PP populations.

10.7 Safety Analyses

Adverse event data will be summarized by treatment group for subjects in the safety population. Safety will be evaluated by presenting summaries of treatment emergent AEs by system organ class and preferred term. Drug related TEAEs, discontinuation of study medication due to TEAEs and all SAEs will also be summarized.

In addition, subject listings will be provided for serious, unexpected, and unanticipated adverse reactions. Any adverse events leading to discontinuation of study drug or death will also be listed for all subjects.

10.8 Other prespecified analyses

10.8.1 Baseline Descriptive Statistics

Demographic characteristics and medical history, adverse events, COVID-19 disease signs and symptoms and treatment compliance will be summarized and compared between treatment groups. The details of the statistical analyses are included in the Statistical Analysis Plan (SAP 3.1).

10.8.2 Planned Interim Analyses

The DSMB will also review the results of the first interim analysis for futility and efficacy once 45% of the clinical events (i.e. 367 clinical recoveries) are obtained and once 45% of the patients are recruited.

The nominal alpha of 0.02 and of 0.0369 at the time of interim and final analysis, respectively. A p-value less than 0.02 (interim) or 0.0369 (final) will be considered to be statistically significant.

Futility will be concluded at interim on the primary efficacy endpoint if Z-value is smaller than 0.58964 (i.e. p-value is larger than 0.6389).

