The unbinding futility rule uses a Power family beta spending function with $\Phi=1.147$ and the probability to stop for futility at interim when there is no difference between the two groups (i.e. $HR=1$) is 73%.

The test for efficacy at interim uses a Power family alpha spending function with $\Phi=1.147$ and if the hazard ratio is truly 1.25, the probability to conclude efficacy at interim is 49%.

This is to be noted that the futility rule is unbinding and that the recommendations whether or not to stop for futility will be done by the Data and Safety Monitoring Board (DSMB) (see section 5.5), upon review of the safety and efficacy data, and not solely based on the futility rule.

10.2.3 Sample Size Determination: Sub-study's Viral Shedding Endpoint: Time to undetectable viral shedding by study day 10

Group sample sizes of approximately 275 subjects in each treatment group (Favipiravir and placebo) in order to obtain 112 undetectable viral shedding events will achieve sufficient power to detect a clinically and epidemiologically meaningful effect size using a two-sided Wilcoxon test at a significance level of 0.05.

10.2.4 Sample Size Justification: Sub-study's Viral Shedding Endpoint: Time to undetectable viral shedding by study day 10

To calculate the required sample size, we used the following assumptions: 1) Follow-up duration per patient of 10 days, 2) Alpha of 0.05, 3) Lost to follow up of 0, 4) Exponential survival rates, 5) Median

time to sustained clinical recovery for the control group of 5 days, 6) Median time to sustained clinical recovery for the favipiravir group of 2.9 days.

In order to detect as statistically significant difference in the median time to undetectable viral shedding of 5 vs. 2.9 days in the control vs. favipiravir group, respectively (HR = 1.7), it is estimated that a total of about 550 subjects (275 per treatment group) in order to obtain 112 clinical events defined as undetectable viral shedding events would be required to achieve a power of 80%.

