10.4 Statistical Analyses: General Approach

Baseline demographic and clinical characteristics and other results will be summarized using descriptive summary statistics. Data collected in the trial will be summarized overall and by treatment arm.

Survival analysis techniques will be used to analyze the time-to-event variables. Failure curves will be constructed for time to positive event using Kaplan-Meier estimates. Time to sustained clinical recovery will be compared using a Gehan Wilcoxon test which gives more weight to early events. Time to a negative event (such as time to death, time to hospitalization) will be compared using the Log-rank test for comparison of survival distributions. Summary tables for safety and efficacy endpoints will include event rates (Kaplan-Meier estimates of event rates), relative risk, confidence interval for the relative risk, the difference in means/rates, the confidence interval for difference in means/rates, and the p-value.

For categorical variables, results within each arm will be summarized with subject counts, percentages, and 95% confidence intervals. The differences between the two treatment arms will be summarized with the difference in percentages and the asymptotic 95% confidence interval for the difference of two percentages.

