11.1.6 Safety Oversight

In addition to the Principal Investigator's responsibility for overall study oversight, safety oversight will be under the direction of a Data and Safety Monitoring Board (DSMB) composed of individuals with the appropriate expertise. Members of the DSMB are independent from the study conduct and free of conflict of interest. The DSMB will operate under the rules of an approved charter written and reviewed at the organizational meeting of the DSMB. After the organization meeting, the DSMB will meet as outlined in the charter. The final meeting scheduled will be outlined in the charter. The DSMB will also review the results of the interim analysis for efficacy described in section of "Statistical Considerations". Stopping rules for safety and efficacy will be specified in the charter.

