13.0 Protocol Amendment History

The table below is intended to capture key changes made between protocol version 5.0 and 5.1

Version 5.0	Version 5.1	Rationale

Site-Subject Remote Visits on Days 1, 2, 3, 4, 5, 6, 7, 8, 9, 10, 11, 12, 14, 17, 21, 24 and 28
 
It is the site responsibility to ensure patients are properly trained on the ePRO requirements and assist the subjects with completing the ePRO diary during the Day 1 visit. Subject interactions will happen on Days 2 through 12, as well as 14, 17, 21, 24, and 28. During the site and subject interactions, the site staff will review the ePRO content for completeness and will work with the subject to ensure complete data entry. This includes reviewing each COVID-19 symptom for severity, temperature, O2 saturation, review of AEs, concomitant medications, IP compliance and saliva sampling compliance (when applicable). Beyond Study Day 12, in the case that subject has not reported on ePRO on a day that a subject visit is not scheduled, the study team will call the subject (unscheduled visit) and ensure that the subject enters the missing information during the phone call. However, if the ePRO system is unavailable or not accessible by the subject for any reason, then the subject should record their information on the paper diary for those days. If the subject used paper diary, during the next site and subject interaction, site staff should complete the data entry on behalf of the subject in ePRO. The study team will collect the paper diary from the subject after they either meet the clinical recovery or the subject reaches Day 28.
	
Site-Subject Remote Visits on Days 1, 3, 5, 7, 9, 14, 17, 21, 24 and 28
 
The study team will be reviewing the data reported by subject to ensure compliance, accuracy and completeness on days 1, 3, 5, 7, 9, 10, 14, 17, 21, 24, and 28. Beyond Study Day 10, once the subject meets the primary efficacy endpoint, the subject is not required to continue the self-assessment and reporting of COVID-19 symptoms. However, the study team, during the remote patient visits will evaluate and report the severity of COVID-19 associated symptoms as per the set frequency mentioned in the table.
	
Change made to address FDA concerns related to site-subject interactions (protocol versions 4.0 and 5.0 have never been implemented). The change reflects protocol version 3.0 which was the last version implemented during the study.

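### The interim futility p-value of 0.6389 does not correspond to the futility Z-value of 0.58964 that it is said to restate; the p-value is the wrong half

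*Combined protocol and SAP*

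**What the plan says.** Section 10.8.2 sets one interim futility criterion for the primary endpoint and writes it in two forms: futility is concluded "if Z-value is smaller than 0.58964 (i.e. p-value is larger than 0.6389"). The synopsis (section 2.1, statistical plan) repeats the same pair. The sentences just before it in 10.8.2 give nominal alphas of 0.02 at the interim and 0.0369 at the final analysis.

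Section 10.2.2 gives the design behind the rule: two-sided alpha of 5%, HR 1.25, 815 events, one interim at 45% information (367 events), and power-family alpha and beta spending, both with parameter 1.147. On power it says: "This will ensure a power of 85% to detect a difference between the two groups". It also gives two operating characteristics. For HR 1, "the probability to stop for futility at interim when there is no difference between the two groups" is put at 73%. For the alternative, "if the hazard ratio is truly 1.25, the probability to conclude efficacy at interim is 49" percent.

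The same section makes the futility rule non-binding. The DSMB's recommendation is to be made "upon review of the safety and efficacy data, and not solely based on the futility rule".

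**The concern.** The two forms are joined as though one restated the other, so they must mark the same point on the same scale. They do not, under either the one-sided or the two-sided convention. A DSMB handed this sentence therefore has two thresholds, and for a range of interim results one says futile and the other does not.

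This sentence is the only place in the documents where a numerical futility cut-off is printed. Section 11.1.6 says "Stopping rules for safety and efficacy will be specified in the charter" and does not name futility there. The SAP (version 3.1) and the charter are not available here, so whether either states the threshold correctly is unknown.

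**Working it through.** **1. Direct conversion**

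- From Z = 0.58964: one-sided p = 1 - Φ(0.58964) = 0.2777; two-sided p = 2 × 0.2777 = 0.5554.
- From p = 0.6389: two-sided |Z| = Φ⁻¹(1 - 0.6389/2) = 0.469; one-sided Z = Φ⁻¹(1 - 0.6389) = -0.356.

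No pairing agrees, and figures printed to four or five digits leave no room for rounding. One arithmetic match does exist: 1 - Φ(0.58964)/2 = 1 - 0.72228/2 = 0.63886, which rounds to 0.6389. That quantity is not a p-value, but it suggests a slip in converting the Z. The origin is an inference.

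**2. Which half does the design support?**

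Inputs from section 10.2.2: two-sided alpha 0.05, beta 0.15, spending exponent 1.147, t = 0.45, non-binding futility.

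- Alpha spent at the interim: 0.05 × 0.45^1.147 = 0.0200 (plan: 0.02), giving an efficacy bound of 2.326.
- Final nominal two-sided alpha, ignoring the futility bound: 0.0369 (plan: 0.0369). Treating futility as binding would give 0.0408.
- Beta spent at the interim: 0.15 × 0.45^1.147 = 0.0600.
- Drift solved for 85% power: 3.195 at full information, so 3.195 × √0.45 = 2.143 at the interim.
- Futility bound = 2.143 + Φ⁻¹(0.0600) = 0.5887. With t = 367/815 it is 0.5899. The plan's value is 0.58964.

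The solved drift implies about 820 events under the log-rank approximation. Fixing the events at exactly 815 instead gives a bound of 0.582 to 0.583. All of these are near 0.590 and far from 0.469 or -0.356. At the solved drift, a cut at 0.469 would spend 0.047 of beta and a cut at -0.356 only 0.006, against the designed 0.060.

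**3. The stated 73% and 49%**

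With Z = 0.58964:

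- HR 1: futility 72.2%, upper efficacy crossing 1.0%, total 73.2%.
- HR 1.25: futility 6.0% to 6.1%, efficacy 42.5% to 42.8%, total 48.6% to 48.8%. The range runs from drift ln(1.25) × √(367/4) = 2.137 to the solved drift.

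The printed 73% and 49% match the totals. As labelled, futility alone at HR 1 is 72.2% and efficacy alone at HR 1.25 is about 43%. That the printed figures are totals is inferred from this match.

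No reading of p = 0.6389 gives both figures. The totals at HR 1 and HR 1.25 would be 69.1% and 47.3% to 47.5% (two-sided, directed), 37.1% and 43.1% to 43.4% (one-sided), or 37.1% and 46.8% to 47.0% (two-sided, undirected).

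**4. Size of the conflict**

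Interim Z is taken as normal with unit variance and mean ln(HR) × √(367/4). Each cell is the probability that the rule signals futility.

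| True HR | Z < 0.58964 | (a) two-sided p, directed (Z < 0.469) | (b) one-sided p (Z < -0.356) |
|---|---|---|---|
| 1.00 | 72.2% | 68.1% | 36.1% |
| 1.10 | 37.3% | 32.9% | 10.2% |
| 1.25 | 6.1% | 4.8% | 0.6% |

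- (a) The halves disagree for Z from 0.469 to 0.590, an observed HR of about 1.050 to 1.063: 4.2% of interims at HR 1, 4.5% at HR 1.10 and 1.3% at HR 1.25.
- (b) They disagree for Z from -0.356 to 0.590, an observed HR of about 0.964 to 1.063: 36.1%, 27.1% and 5.5%.
- (c) A two-sided p read without direction signals futility only when |Z| < 0.469. It disagrees with the Z rule in 36.1% of interims at HR 1. At HR 0.80 it signals futility in 4.3%, against 99.7% for the Z rule.

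Power at 815 events and HR 1.25, if the rule is followed: 84.8% with Z, 85.5% with (a), 87.0% with (b). With no futility stop it is 87.1%.

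**The case against.** The strongest reply is that this is a small slip in a bracket. Z is the stated criterion, the p-value only glosses it, and the match to 1 - Φ(Z)/2 suggests a botched conversion rather than a rival threshold. The neighbouring p-values (0.02 and 0.0369) are on the two-sided scale and the Z wording is directional, so reading (a) is the natural one. On that reading the conflict is 4.2% of interims at HR 1 and power moves by less than a point. The 36.1% figures need readings with less support in the text. The intended Z can also be recovered from the spending function and power in section 10.2.2.

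Most of this stands, and it limits the severity. It does not make the sentence right: the p-value is false under every convention, it appears twice, and a DSMB should not have to re-solve the design to learn which half to use.

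Two further objections stand in part. The agreement to 0.589 to 0.590 uses a drift solved for exactly 85% power; at 815 events it is 0.582 to 0.583, so the fit is close rather than exact. And the 73% and 49% labels are a separate matter from the p-value. The 73% is within a point of the futility figure, but the 49% is about six points above efficacy alone, so it does fail as labelled. Section 11.1.6 not naming futility does not show that the charter omits it.

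**Conclusion.** The concern holds: the futility p-value of 0.6389 is wrong, and the Z-value of 0.58964 is the threshold the plan's own design supports. The conversion itself rests on no assumption. The size depends on the unstated p-value convention: about 4% of interims at HR 1 on the most natural reading, and 36.1% on the other two.

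The probabilities assume 367 interim events, 1:1 allocation, proportional hazards, and a test statistic that behaves like a log-rank Z. Section 10.4 specifies otherwise for the analysis: "Time to sustained clinical recovery will be compared using a Gehan Wilcoxon test which gives more weight to early events". The Z-to-p mismatch does not depend on that approximation.

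Because the rule is non-binding, type I error, the 0.02 and 0.0369 limits, the sample size and the primary analysis are untouched. This should be fixed, but it does not threaten the trial's conclusions. Section 13.0 refers to "version 3.0 which was the last version implemented during the study", and the documents do not say whether the interim had been held. If it had, what needs correcting is the record of which threshold was applied.

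**What to change.** - In sections 2.1 and 10.8.2, keep Z < 0.58964 and state that positive Z means faster recovery on favipiravir. Delete the p-value, or replace it with one-sided p > 0.2777 and name the sidedness. Substituting two-sided 0.5554 would not be enough, because a result clearly favouring placebo can have a small two-sided p.
- In section 10.2.2, check 73% and 49% against the design output. If they are total early-stopping probabilities, relabel them so. Otherwise restate them from that output; the recomputation here gives about 72% (futility at HR 1) and 43% (efficacy at HR 1.25).
- Align the SAP and the DSMB charter. If the interim has been held, record which threshold the DSMB was given.

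The cost is one line in two places, two labels, and matching text in the SAP and charter. The design, sample size and alpha do not change.
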